1.3.1 Galderma Chin Retrusion Scale (GCRS)

GCRS is a validated Four-Point scale assessing the Chin Retrusion from no retrusion (0) to severe retrusion (3) as described below.

The Blinded Evaluator will rate the subject's Chin Retrusion using the GCRS at screening, baseline, 3, 6, 9 and 12 months in Treatment Group; and at screening, baseline 3 and 6 months after randomization, as well as 3, 6, 9 and 12 months after last treatment in Control Group.

The Treating Investigator will do the GCRS evaluation at all visits in each group.

Table 1. The Galderma Chin Retrusion Scale.

GCRS	
0	No Retrusion: The most anterior portion of the chin is at or near a vertical line drawn from the vermillion border of the lower lip.
1	Mild Retrusion: The most anterior portion of the chin is clearly recessed, but less than midway, between vertical lines drawn from the vermillion border of the lower lip and the oral commissure.
2	Moderate Retrusion: The most anterior portion of the chin is recessed approximately midway between vertical lines drawn from the vermillion border of the lower lip and the oral commissure.
3	Severe Retrusion: The most anterior portion of the chin is clearly posterior to the midway point between vertical lines drawn from the vermillion border of the lower lip and the oral commissure.

CCI

 GALDERMA	<small>Title</small> Statistical Analysis Plan 43CH1627 - Chin	<small>Doc id</small> MA-38115
--	--	--

CCI

1.4 Effectiveness endpoints

1.4.1 Primary effectiveness endpoint

Percentage of responders based on the GCRS as measured by the Blinded Evaluator at 6 months (after last treatment in Treatment Group and after randomization in Control Group).

A responder is defined as a subject who achieves a score of at least 1 point improvement from baseline to 6 months on the GCRS.

1.4.2 Secondary effectiveness endpoints

Secondary effectiveness endpoints include:

- (i) **Percentage of responders as measured by the Blinded Evaluator at 3, 9 and 12 months after last treatment in Treatment group and at 3 months after randomization as well as 3, 6, 9 and 12 months after last treatment in Control group**

A responder is defined as a subject who achieves a score of at least 1 point improvement from baseline on the GCRS.

 GALDERMA	Title Statistical Analysis Plan 43CH1627 - Chin	Doc id MA-38115
--	---	---------------------------

(ii) Percentage of responders as assessed by the Treating Investigator at each follow-up visit

The follow-up assessments will be done 3 months, 6 months, 9 months and 12 months after last treatment for the Treatment Group, and at 3 months and 6 months after randomization as well as 3 months, 6 months, 9 months and 12 months after last treatment for Control Group.

A responder is defined as a subject who achieves a score of at least 1 point improvement from baseline on the GCRS.

CCI

1.5 Safety assessments

The methods for collecting safety data are described in Section 8 of the Clinical Study Protocol (CSP) CCI

Adverse Events (AE), Serious Adverse Events (SAE). Laboratory assessments will be performed at screening and at 6 months after last treatment or at early termination if termination occurs before 6 months visit after last treatment for all subjects. In Control Group, it will also be taken at 6 months visit before treatment. ECG will also be assessed, but at screening only.

A two-point scale (“Yes” or “No” response) will be used for the causality assessments. The Treating Investigator should be asked to indicate a response to each of the following questions in the eCRF:

- “Do you consider that there is a reasonable possibility that the event may have been caused by the study product?”
- “Do you consider that there is a reasonable possibility that the event may have been caused by the study product injection procedure?”

If any of these questions is answered with a ‘Yes’, the AE will be considered related. These assessments will also be reviewed by the Sponsor. In the case of a disagreement, the AE will be classified as “Related”.

[figure not shown]
1.6 Safety endpoints

Safety endpoints include:

(v) Incidence, intensity, duration, and onset of related Adverse Events (AEs) collected throughout the whole study

 GALDERMA	<small>Title</small> Statistical Analysis Plan 43CH1627 - Chin	<small>Doc id</small> MA-38115
---	--	--

CCI

Effective date: 2018-08-23 03:02

Effective

Version: 1.0

 Title **Statistical Analysis Plan 43CH1627 - Chin** Doc id **MA-38115**

Effective date: 2018-08-23 03:02

Effective

Version: 1.0

2 Statistical Methods

2.1 General methods

All statistical analyses, including summary tables and data listings, will be performed using the SAS® system (version 9.4 or later).

In general, effectiveness, safety, demography, subject characteristics, and treatment related variables will be presented using descriptive statistics. Continuous data will be summarized using n (number of observations), mean, standard deviation, median, minimum and maximum value, while categorical data will be presented by frequency and percentage. Graphs may be used as appropriate.

All statistical testing will be two-sided and performed at a significance level of 5%. Confidence intervals will be 2-sided and constructed using 95% confidence level.

Any change made to the finalized statistical analysis plan (SAP) will be documented in the Clinical Study Report (CSR).

2.2 Analysis Populations

The following populations will be defined:

- Safety Includes all subjects who were treated with Restylane Defyne or randomized to no-treatment group. Subjects are analyzed based on the as treated principle
- Full Analysis Set (FAS) Includes all subjects who were treated with Restylane Defyne or randomized to no-treatment group. Subjects are analyzed according to the randomization assignment.
- Per Protocol (PP) Includes all subjects in FAS that comply to the protocol procedures with no deviations that can affect the evaluation of the primary variable

The FAS population is the primary population for all effectiveness analyses. All safety analyses will be based on the Safety population.

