4.4.2 Blinding

Only the evaluator will be blinded to treatment.

The Blinded Evaluator shall not be allowed to retrieve study supplies or to be present during opening of the study supplies or injections. The Treating Investigator or the subjects are not allowed to discuss treatments with the Blinded Evaluator. All documents with information on study products and randomization assignment shall be kept in a separate binder not available to the Blinded Evaluator.

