4.4.3 Emergency unblinding

Not applicable as the Treating Investigator is unblinded.

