10.2 Analysis Populations

The following populations will be defined:

- Safety Includes all subjects who were treated with Restylane Defyne or randomized to no-treatment group. Subjects are analyzed based on the as treated principle.
- Full Analysis Set (FAS) Includes all subjects who were treated with Restylane Defyne or randomized to no-treatment group. Subjects are analysed according to the randomisation assignment.
- Per Protocol (PP) Includes all subjects in FAS that comply to the protocol procedures with no deviations that can affect the evaluation of the primary variable.

The FAS population is the primary population for all effectiveness analyses. All safety analyses will be based on the Safety population.

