10.6 Handling of Missing Data

Number of missing values will be summarized and reported as appropriate.

Different assumptions regarding the missing data will be used. For the primary effectiveness analysis, missing values in the FAS will be assumed to be missing due to lack of effect. Therefore missing data up to the Month 6 visit will be imputed using the baseline observation carried forward (BOCF) method. As an alternative approach, missing data will be assumed to be unrelated to treatment effect. CCI

More details will be given in the SAP. Both of these alternatives will estimate the effectiveness of the treatment policy (irrespective of use of unallowable treatments, procedures, or medications) rather than the true, clinical treatment effect.

To obtain an estimate of the true clinical treatment effect, the primary effectiveness analysis will be performed using the PP.

All other endpoints will be analysed on available data, i.e. no imputations will be done.

| | | |
|--|--|---------------------------|
|  GALDERMA | Title 43CH1627 Clinical Study Protocol | Doc id MA-34970 |
|--|--|---------------------------|

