2.3 Study subjects

2.3.1 Subject disposition

The number of subjects in each study population (i.e. FAS, PP, and Safety) will be summarized by site and in total.

The disposition of subjects (including reasons for screening failures and withdrawals) will be presented by treatment group and in total. Subject accountability will be presented by treatment and visit.

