2.4 Effectiveness analysis

2.4.1 Datasets analyzed

[figure not shown]
All effectiveness variables will be analyzed using the FAS population. The primary analysis will be repeated using the PP population. If it is deemed necessary, other analyses will be repeated using the PP population.

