**Table A 17. GCRS responder rate by treatment at Month 6, Blinded Evaluator (FAS)**

Time point	Treatment group	# of subjects in FAS	# of responders	Proportion of responders	95% confidence interval	P-value
6 month after last treatment	Restylane Defyne	xx	xx	x.xx	x.xx, x.xx	
6 month after randomization	Control	xx	xx	x.xx	x.xx, x.xx	
Difference	-			x.xx	x.xx, x.xx	x.xx

Note: Subjects with a missing GCRS have their values imputed using BOCF at Month 6

Note: Responder is defined as a subject with an improvement of at least one grade on the GCRS from baseline

Note: Responder rate is calculated as the number of Responders divided by the number of subjects in the FAS population for the specific treatment group.

Note: P-values for the difference in proportions are based on the Fisher's Exact test

Note: 95% Confidence Intervals are two-sided and calculated using the binomial distribution

Table A 18. GCRS responder rate by treatment at Month 6, Blinded Evaluator (PP)

As Table A 17.

Note: No imputation is used for the PP analysis. Only subjects with complete data are included.

Note: Responder is defined as a subject with an improvement of at least one grade on the GCRS from baseline

Note: Responder rate is calculated as the number of Responders divided by the number of subjects in the FAS population for the specific treatment group.

Note: P-values for the difference in proportions are based on the Fisher's Exact test

Note: 95% Confidence Intervals are two-sided and calculated using the binomial distribution

Table A 19. Sensitivity analysis for the GCRS responder rate by treatment at Month 6, Blinded Evaluator (FAS)

As Table A 17.

Note: Subjects with a missing GCRS have their values imputed using the hot deck method at Month 6

Note: Responder is defined as a subject with an improvement of at least one grade on the GCRS from baseline

Note: Responder rate is calculated as the number of Responders divided by the number of subjects in the FAS population for the specific treatment group.

Note: P-values for the difference in proportions are based on the Fisher's Exact test

Note: 95% Confidence Intervals are two-sided and calculated using the binomial distribution

Table A 20. Logistic regression, Blinded Evaluator (FAS)

Parameter	Coefficient	SE	Wald Chi-Square	Degrees of freedom	P-value
Baseline GCRS	x.xx	x.xx	x.xx	x	x.xx
Treatment Group	x.xx	x.xx	x.xx	x	x.xx

Title

Statistical Analysis Plan 43CH1627 - Chin

Doc id

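### The FAS takes controls on randomization but Treatment Group subjects only if injected, so no readable analysis compares the groups as randomized

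*SAP*

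**What the plan says.** The SAP definition of the FAS (2.2) is: "Includes all subjects who were treated with Restylane Defyne or randomized to no-treatment group. Subjects are analyzed according to the randomization assignment". Protocol 10.2 differs only in spelling: "Includes all subjects who were treated with Restylane Defyne or randomized to no-treatment group. Subjects are analysed according to the randomisation assignment". The Safety population has the same entry sentence and is analysed as treated. The PP population is drawn from within the FAS.

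On the analyses, SAP 2.4.1 states: "All effectiveness variables will be analyzed using the FAS population. The primary analysis will be repeated using the PP population". The note to Table A 17, the primary result, fixes the denominator: "Responder rate is calculated as the number of Responders divided by the number of subjects in the FAS population for the specific treatment group". The hot deck analysis (Table A 19) and the logistic regression (Table A 20) are both labelled FAS.

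On what is being estimated, Protocol 10.6 describes BOCF and an alternative missing-data approach and says: "Both of these alternatives will estimate the effectiveness of the treatment policy (irrespective of use of unallowable treatments, procedures, or medications"; the parenthesis closes there. The same section gives the estimate of the true clinical effect to the PP population.

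On blinding, Protocol 4.4.2 says "Only the evaluator will be blinded to treatment", and Protocol 4.4.3, on emergency unblinding, says "Not applicable as the Treating Investigator is unblinded". The Treatment Group baseline visit (Protocol 4.8.1.2) lists randomization ahead of treatment.

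**The concern.** Membership of the primary analysis set depends on a post-randomization event in one arm and on randomization alone in the other. The clause about analysing by randomization assignment settles the arm in which a member is counted. It does not settle who is a member.

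Both the subject and the Treating Investigator know the allocation before the needle is used, so a decision not to inject can follow that knowledge. The subject concerned is then removed from the Treatment Group only. SAP 2.4.2 calls BOCF conservative because missing subjects count as non-responders, but BOCF cannot reach a subject who is outside the FAS.

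At stake are the Treatment Group responder rate, which is the headline estimate in a study meant to support registration in China (Protocol 2.5), and the claim that this estimate reflects a treatment policy. The significance test is much less exposed.

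**Working it through.** **Who is in each readable analysis**

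| Analysis | Set | Includes a randomized, uninjected Treatment Group subject? |
|---|---|---|
| Primary, BOCF (A 17) | FAS | No |
| Repeat of primary (A 18) | PP, within FAS | No |
| Hot deck (A 19) | FAS | No |
| Logistic regression (A 20) | FAS | No |
| Disposition and population counts (A 1, A 2) | Screened / all randomized | Counted, but no outcome compared |

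**Inputs from the documents.** About 148 are randomized 3:1, so 148 × 3/4 = 111 and 148 × 1/4 = 37, which agrees with SAP 2.7. The primary test is a two-sided Fisher's exact test at 5% (SAP 2.1 and 2.4.3). The assumed response rates and power are redacted, so the sample size itself cannot be rebuilt.

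**Assumptions.** k = number of the 111 never injected; p = response rate among the injected, 50–80%; control responders 2, 4 or 7 of 37. The readable text gives none of these.

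**Shift in the Treatment Group rate.** Let r be the number of responders among the 111 − k injected, so p = r/(111 − k). If the uninjected have no Month 6 value and count as non-responders under BOCF:

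shift = r/(111 − k) − r/111 = p × k/111

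| k | p = 50% | p = 80% |
|---|---|---|
| 1 | 55/110 − 55/111 = 0.5 points | 88/110 − 88/111 = 0.7 points |
| 2 | 54/109 − 54/111 = 0.9 | 87/109 − 87/111 = 1.4 |
| 5 | 53/106 − 53/111 = 2.3 | 85/106 − 85/111 = 3.6 |

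At about 75% response, k = 2 gives 82/109 = 75.2% against 82/111 = 73.9% (1.4 points), and k = 5 gives 80/106 = 75.5% against 80/111 = 72.1% (3.4 points).

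If instead every uninjected subject attends Month 6 and responds at an assumed control-like rate of 4/37, the shift becomes (p − 4/37) × k/111. The two 75% examples fall to 1.2 and 2.9 points.

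**Effect on the test (uninjected counted as non-responders)**

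- With 4/37 control responders and p of 50–80%, the largest all-randomized p-value is 0.00006 for k up to 8 and 0.0003 for k up to 17.
- With 2, 4 or 7 of 37 control responders, no Treatment Group count changes the verdict at k = 1 or k = 2.
- Reversals need a result near the boundary. With k = 5 and 4/37 controls, 29/106 (27.4%) gives p = 0.043 on the FAS, and 29/111 gives p = 0.068 on all randomized. With k = 3 and 7/37 controls, 40/108 (37.0%) gives p = 0.045, and 40/111 gives p = 0.067.

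**The case against.** The best case for leaving the definition alone has four parts.

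**The treatment-policy sentence is narrower than it looks.** Its parenthesis in Protocol 10.6 names unallowable treatments, procedures and medications, not failure to receive the injection. That is fair as far as it goes: the two texts do not contradict each other word for word. But 10.6 gives the treatment-policy reading to the FAS approaches and the true clinical effect to PP. A set that requires receipt of treatment in one arm does not fit the first role.

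**Few subjects should be affected.** Injection is planned for Day 1, the pregnancy test (when required) and vital signs come before randomization, and everyone enrolled is seeking augmentation. Disappointment with the allocation is more likely among controls, who stay in the FAS. This stands, and it is why the expected size is small. The documents give no expected number.

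**The verdict hardly moves.** This also stands. The two reversals shown need 27.4% or 37.0% response, outside the 50–80% assumed here, and a reversal at k = 1 needs at least 13 of 37 controls to respond.

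**The exclusions would be visible.** SAP 2.3.1 says: "The number of subjects in each study population (i.e. FAS, PP, and Safety) will be summarized by site and in total". That is not by arm, but subtracting the Table A 17 denominator from the randomized count in Table A 1 gives the number by arm. Table A 3 tracks attendance at the initial treatment visit, and Table A 5 lists each withdrawn subject with group and treatment date. A careful reader could find these subjects, but would still have no prespecified result that includes them.

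**Conclusion.** The concern holds. The rule as written makes a one-arm exclusion after an unblinded allocation, and every readable effectiveness analysis inherits it. That the definition works this way is clear from the text; how many subjects it would affect is unknown.

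The expected effect is a modest overstatement of the Treatment Group responder rate: 0.5–0.7 points for one uninjected subject and 2.3–3.6 for five. This rests on 50–80% response among the injected and on non-response among the rest. The direction is expected, not certain, because an uninjected subject who attends Month 6 could be scored a responder. The consequence is mainly for the reported rate and the estimand, and only in borderline results for the test. Redacted text might contain another analysis, so the finding is limited to what can be read. It should be corrected, but it does not by itself threaten the trial's conclusion.

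**What to change.** Define the FAS in Protocol 10.2 and SAP 2.2 as all randomized subjects, analysed as randomized. Treatment Group subjects who were never injected have no last treatment to count from, so time their Month 6 from randomization. Use the observed Blinded Evaluator GCRS where there is one, and otherwise BOCF, which makes them non-responders. Leave the Safety population as it is. Report the number randomized but not treated by arm, for example by adding arm columns to Table A 2.

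This needs a written protocol amendment with IEC approval (Protocol 12.3), a SAP revision, and a clause in the Month 6 endpoint wording (Protocol 3.2.1; SAP 1.4.1 and 2.4.3). The only added visit is a Month 6 assessment for a never-treated subject who stays in follow-up. The reported rate may fall slightly; if everyone is injected, results are identical.

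If an amendment is not wanted, the minimum is an all-randomized sensitivity version of Table A 17 with the same handling of the never-treated, specified before outcomes are known. That needs a SAP change alone.

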2.3 Study subjects

2.3.1 Subject disposition

The number of subjects in each study population (i.e. FAS, PP, and Safety) will be summarized by site and in total.

The disposition of subjects (including reasons for screening failures and withdrawals) will be presented by treatment group and in total. Subject accountability will be presented by treatment and visit.

2.3.2 Withdrawals and Protocol deviations

All withdrawn subjects will be listed individually, including at least subject number, date and reason for withdrawal, and last visit performed. Subjects with CSP deviations will be listed individually, including subject number and observed deviation. Depending on the seriousness of the deviation, subject might be excluded from the PP population, which shall be documented prior to database lock.

 GALDERMA	Title Statistical Analysis Plan 43CH1627 - Chin	Doc id MA-38115
--	---	---------------------------

For this study, the protocol deviations that will exclude subjects from PP are identified (but not limited to) in Table 3 below.

Table 3. Protocol deviations

	Deviation
GENERAL	
	Visit out-of-window
	* Follow-up at Month 6 after last treatment performed earlier than 1 week before or later than 2 weeks after the scheduled visit for the treatment group
	* Follow-up at Month 6 after randomization performed earlier than 1 week before or later than 2 weeks after the scheduled visit for the control group
EFFECTIVENESS	
	Primary effectiveness endpoint
	* Pre-treatment GCRS by blinded evaluator not done
	* GCRS by blinded evaluator missing at Month 6 after last treatment for treatment group
	* GCRS by blinded evaluator not done at Month 6 after randomization for control group
	Treatment
	* Wrong treatment given at baseline
OTHER	
	Inclusion/exclusion criteria
	* Violate any inclusion or exclusion criteria considered to have substantial effect on the primary effectiveness endpoint
	Concomitant medication/procedures
	* Take any prohibited concomitant medication/procedures considered to have substantial effect on the primary effectiveness endpoint

Deviations from the SAP will be documented in the CSR.

2.3.3 Demographic characteristics

Subject demographic and baseline characteristics data will be summarized for the FAS population by treatment group and in total.

2.3.4 Medical and surgical history, concomitant medication/procedures

All summaries will be done by treatment group based on the FAS population. Concomitant medications will be coded using the World Health Organization (WHO) Drug Dictionary. Medical History will be coded according to MedDRA.

The number and percent of subjects reporting medical history, and the number of events will be summarized by system organ class (SOC), in total and for ongoing events.

The number and percentage of subjects reporting concomitant medications will be summarized by treatment. In addition, the number and percent of subjects reporting concomitant medication, and the number of drugs (total number and the number of ongoing drugs), will be summarized by

	
Title Statistical Analysis Plan 43CH1627 - Chin
	
Doc id MA-38115

--	---	-----------------------------------

reason. The same summary will be done for concomitant procedures/treatments. Also, the number and percent of subjects, and the number of drugs, will be summarized by ATC code. Concomitant medications that started due to an AE will be summarized separately.

